5.0 STUDY DRUG SUPPLY

Based on the retrospective phase of the study, on average 82% of patients received 200mg or less of sugammadex, 17% received between 200 and 500mg, and the remaining 1% received more than 500mg. The study drug supply will reflect these ratios; 80% of vials supplied will be 200mg, and the remainder will be 500mg vials.

6.0 STUDY DESIGN

In order to allow for a learning curve associated with the introduction of sugammadex we will not include any patients for one year after sugammadex introduction.

Creation and implementation of a pathway to prevent postoperative respiratory dysfunction:

In order to improve outcomes for high-risk patients who receive general anesthesia and paralysis we will design and implement a perioperative decision support system which will identify high-risk patients and provide best practice recommendations via electronic clinical decision support reminders. While the exact parameters of the pathway will be designed based upon feedback from a group of quality leaders in the department (see Study Procedures below), in general the pathway will function as follows.

Patients will be identified based upon the aforementioned selection criteria. Patients meeting one or more of the following: Undergoing surgery at RRUMC OR, Santa Monica OR, obstructive or restrictive lung disease in EMR, obstructive sleep apnea, preoperative O2 saturation <95% (average/median of 12 hours before surgery), BMI>40, acute respiratory infection within 1 month prior to surgery, previous history of airway pathology; or two or more of the following: BMI>35, multiple intubation attempts, surgical duration >2 hours, upper abdominal surgery, intrathoracic surgery or airway/head and neck surgery, or most recent Hb (within 6 months) <10. Patients will be excluded if they are less than age 18, have co-existing renal disease with a GFR<30, neuromuscular disease, are pregnant or breastfeeding at the time of surgery, have an allergy to sugammadex or rocuronium, or patients who are expected to remain intubated after surgery or expected to leave the operating room with a tracheostomy in-situ.

When the anesthesiologist completes the preoperative evaluation for a patient who is flagged as having either respiratory disease or OSA and will receive general anesthesia, the anesthesiologist will receive a pop-up window reminding them of the best practice guidelines for pulmonary management in high-risk patients. As part of the study roll-out we will present these guidelines with our quality committee, but we anticipate that they will suggest 1) use of sugammadex to reverse neuromuscular blockade if rocuronium was used 2) use of objective train of four monitoring throughout the case and to confirm reversal 3) use of a tidal volume of 6-8 cc/kg 4) use of at least 5 cmH₂O of PEEP 5) positioning the head of the bed >30° after extubation.

7.0 SAMPLE SIZE

It is estimated that the respiratory depression pathway will recommend sugammadex for all patients in the medium or high-risk groups as well as some patients in the low risk group. The estimated anticipated sample size is 6,500 patients.

8.0 CLINICAL DECISION SUPPORT PATHWAY

The final clinical decision support pathway for clinician adherence involves preoperative and intraoperative phases. Clinicians will be trained prior to study go-live to ensure awareness and understanding of pathway procedures.

Preoperative Phase

1) Physicians/CRNAs will receive an alert identifying the patient as high-risk for postoperative pulmonary complications and the reason for the designation.
2) The notification will remind the provider to pick up study sugammadex from the OR pharmacy.
3) The notification will display the patient specific lung protective ventilation (LPV) parameters.

Intraoperative Phase

1) There will be a notification reminding the provider to get the study sugammadex.
2) If the patient has mechanical ventilation and the parameters are outside the LPV guidelines (5-7cc/kg and at least 5 of PEEP) an alert will pop up with the LPV recommendations.
3) If non-depolarizing NMB was given and it has been more than 30 minutes since TOF was documented (and last documentation was <100% and no subsequent NMB was given), then a popup will recommend checking twitches (note we will have the twitch monitor automatically populate into CC).
4) Reverse with Sugammadex.

9.0 STUDY HYPOTHESIS

- 1) Sugammadex is a direct reversal agent for rocuronium that has been shown to be superior to reversal with neostigmine. We hypothesize that the introduction of sugammadex into clinical practice at our institution results in a decrease in respiratory dysfunction in the PACU.
- 2) Creation and implementation of a pathway that applies best practices (including reversal with sugammadex) to patients who have obstructive sleep apnea (OSA), or preexisting respiratory disease will decrease the incidence of short-term respiratory complications

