26.0 ESTIMATED SAMPLE SIZE

Sugammadex was introduced into clinical practice at UCLA in May of 2016, thus we have well more than one year of data prior to and after sugammadex introduction. As a result, the power analysis and sample size discussion is roughly the same for the retrospective and prospective portions of this study.

Over the previous one year period, approximately 13,000 patients received general anesthesia with the use of either rocuronium or vecuronium. Given that our surgical volumes are stable we would expect the sample size for the prospective portion of our study to be roughly the same. The table below contains the risk stratification for this group.

To determine the study power, we analyzed the incidence of the primary and secondary outcomes for our historical population. Because there is no current pathway, we are unable to explicitly model the power for performance of identified best practices however the power for the primary outcome as well as secondary outcomes were calculated.

In order to determine our power for the study variables patients were separated into low, medium, and high-risk groups. Low risk patients were those who had no prior documentation of OSA or respiratory disease prior to surgery. Medium risk patients were those with either OSA or respiratory disease and high risk patients were those with both diseases. It is important to note that this classification is significantly simplified as compared to the analysis that will be performed for either the retrospective or prospective studies as it fails to account for key factors such as severity of illness. Nonetheless we believe that these simplifications have the effect of underestimating the potential power and thus the below serves as a conservative estimate.

Table 1. Number of patients in low, medium, and high risk groups from 12/2017- 11/2018	
Risk Class	Number of Patients
Low – No disease	9730
Medium – OSA or Respiratory Disease	2952
High – OSA and Respiratory Disease	445
Total	13,127

Note: The risk classifications above are simplified versions of the true risk classifications to be used in the actual study

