At this point, we estimate that the pathway will recommend sugammadex for all patients in the medium or high-risk groups as well as some patients in the low risk group (i.e. those patients requiring deep neuromuscular blockade to facilitate surgical conditions such as robotic procedures, free flap cases and others). Given the large number of patients, Merck would supply one vial of study drug for each patient. Thus the total amount of study drug would be no more than 6,500 patients for the one year intervention time.

Given 1 year of data, we observed an overall average PACU discharge time of 152.54 minutes (SD=623.86). With one year of post-data, we are adequately powered (90%) to pick up a reduction in PACU discharge time as small as 27.04 (two-sample t-test, alpha=0.025). Since the current difference in PACU discharge time between low and high risk groups is 67.52 (subtracting 216.62-149.10, see table), we feel the 27.04 minimally detectable difference gives us a great chance of detecting a meaningful difference.

Given 1 year of data (pre-period), we observed the rate of patients with any time SpO2<90% was 4.6% (574/12,467). With one year of post-data, we are adequately powered (90%) to pick up a reduction in this rate if it decreases to around 3.7% in the post (chi-square test, alpha=0.025). Since the current difference in patients with any time with SpO2<90% between low and high risk patients is 5.2% (subtracting 9.2%-4.0%), we feel the minimally detectable difference of 3.7% (4.6%-3.8%) is feasible.

Table 2.

	suppl O2, mean (SD)	PACU disch. Time, mean (SD)	Reintubation, freq (%)	Unplanned upgrade, freq (%)	SpO2<90%, freq (%)	SpO2<95%, freq (%)
OVERALL(n=13,277)	74.81 (241.82)	152.54 (623.86)	89 (0.7%)	138 (1.0%)	574 (4.6%)	6510 (52.3%)
low (n=9,841)	74.48 (280.55)	149.10 (599.78)	63 (0.6%)	111 (1.1%)	372 (4.0%)	4603 (50.0%)
medium(n=2,997)	74.98 (95.67)	154.43 (536.58)	23 (0.8%)	22 (0.7%)	164 (5.8%)	1658 (58.8%)
high (n=439)	79.54 (88.44)	216.62 (1321.46)	3 (0.7%)	5 (1.1%)	38 (9.2%)	249 (60.9%)
Smallest detectable difference (90% power)	9.61	24.84	0.4%	0.4%	3.8%	50.3%

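### The stated 90% power belongs to the whole one-year surgical cohort; the prospective pathway comparison, in about 6,500 patients or in OSA/respiratory patients only, does not have it

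*Combined protocol and SAP*

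**What the plan says.** Hypothesis 2 in protocol section 9.0 predicts that a best-practice pathway applied "to patients who have obstructive sleep apnea (OSA), or preexisting respiratory disease will decrease the incidence of short-term respiratory complications". Section 6.0 describes the reminder as appearing "for a patient who is flagged as having either respiratory disease or OSA and will receive general anesthesia".

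Other places describe a wider group. The synopsis names the two diseases only as examples of higher risk. Section 12.1 also admits patients on BMI, haemoglobin, type and length of surgery, recent infection and airway history. Section 26.0 expects the pathway to recommend sugammadex for all medium- and high-risk patients "as well as some patients in the low risk group (i.e. those patients requiring deep neuromuscular blockade". The synopsis and section 7.0 put the prospective sample at about 6,500.

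For the power calculation, section 26.0 defines the risk classes by disease: "Low risk patients were those who had no prior documentation of OSA or respiratory disease prior to surgery", and "Medium risk patients were those with either OSA or respiratory disease and high risk patients were those with both diseases". The calculation itself uses the top row of Table 2, "OVERALL(n=13,277" patients, where "we observed an overall average PACU discharge time of 152.54 minutes (SD=623.86" minutes), and 574 of 12,467 patients (4.6%) had SpO2<90%. Section 26.0 claims 90% power for 27.04 minutes and for a fall to about 3.7%, at alpha 0.025. The SAP gives 24.84 minutes and 3.8% at alpha 0.05. Both say the power discussion is roughly the same for the retrospective and prospective parts.

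**The concern.** The power is quoted for one population and the pathway hypothesis is stated for another. About three quarters of the patients behind the 90% figure have neither disease named in hypothesis 2, and the cohort is about twice the planned pathway sample. A reader would take the prospective comparison to be well powered for the printed differences.

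If it is not, a null result says little about the pathway. A positive whole-cohort result could come largely from patients outside hypothesis 2. Pooling also dilutes. If only the diseased quarter benefited, an overall change of 27.04 minutes would need 27.04 / (3,436/13,277) = about 104 minutes in them. An overall fall of 0.9 points would need 0.9 / (3,241/12,467) = about 3.5 points.

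**Working it through.** **Inputs.** The overall and group rows of Table 2; alpha 0.025, two-sided (the protocol does not state sidedness, but two-sided reproduces its figures); equal one-year periods.

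**Formulas.**
- Means: SE = SD × √(2/n); detectable difference at 90% power = SE × (2.241 + 1.282) = SE × 3.523; power = Φ(d/SE − 2.241).
- Proportions: the same form, with the pooled variance under the null and no continuity correction.

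**1. The plan's own figures reproduce with the whole cohort.**
- PACU time: SE = 623.86 × √(2/13,277) = 7.657. Detectable difference = 26.97 min (stated 27.04). Power at 27.04 = Φ(3.531 − 2.241) = 90.1%.
- The SAP version at alpha 0.05: 7.657 × 3.242 = 24.82 min (stated 24.84).
- SpO2<90%, 4.6% to 3.7%, 12,467 per period: SE = 0.00253; power = Φ(3.563 − 2.241) = 90.7%.

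So the arithmetic is sound for the whole cohort.

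**2. Who is in that cohort.** Low risk: 9,841/13,277 = 74.1% in Table 2 and 9,730/13,127 = 74.1% in Table 1. Medium + high: 2,997 + 439 = 3,436 (25.9%).

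**3. Wider pathway cohort, 6,500 per period, same SD, rate and effects.**
- PACU time: SE = 623.86 × √(2/6,500) = 10.943. Power at 27.04 = Φ(2.471 − 2.241) = 59%. Detectable difference = 38.6 min.
- SpO2<90%: SE = 0.00350. Power for 4.6% to 3.7% = Φ(2.573 − 2.241) = 63%. Detectable post-period rate about 3.4%.
- Setting the full baseline year against 6,500 pathway patients gives 73% (13,277 v 6,500, PACU time) and 75% (12,467 v 6,500, SpO2<90%).
- At the SAP's alpha 0.05 and its smaller effects, 6,500 v 6,500 gives about 62% for each outcome.

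**4. OSA or respiratory disease only, SpO2<90%.** The denominators are not printed. From the rounded percentages, 164/0.058 + 38/0.092 = 2,828 + 413 = 3,241, so the rate is 202/3,241 = 6.2%.
- Same absolute fall (0.9 points): SE = 0.00580; power = Φ(1.552 − 2.241) = 25%.
- Same relative fall (3.7/4.6, so 6.23% to 5.01%): SE = 0.00572; power = Φ(2.131 − 2.241) = 46%.
- 90% power requires about 6.2% to 4.3%, a 31% relative fall.
- Back-calculating from the SpO2<95% column gives 3,227 patients and 6.3%; power is then 24% and 46%.

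**5. Same patients, PACU time.** Combining the two groups' means and SDs gives SD 688.6. The same pooling over all three groups returns 152.54 and 623.99, against 152.54 and 623.86 in Table 2. SE = 688.6 × √(2/3,436) = 16.61. Power at 27.04 = Φ(1.628 − 2.241) = 27%. Detectable difference = 58.5 min. With SD 623.86 these become 33% and 53.0 min.

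**The case against.** **Hypothesis 2 may be shorthand.** The synopsis gives the two diseases as examples, and the eligibility criteria are wider. This is fair, and it makes the 3,436-patient figures a subgroup result if the hypothesis is reworded. It does not rescue the stated power, because the wider cohort is about 6,500 and step 3 then applies. Section 26.0 calls 6,500 a ceiling on drug supply, which would make step 3 generous rather than harsh.

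**The effect may be larger in diseased patients.** It may. Section 4.0 cites an earlier decision-support project with a larger reduction in high-risk patients (20%) than overall (11%), for a different outcome. A relative fall of about 31% in SpO2<90% would restore 90% power. The plan neither states nor justifies such an effect. The protocol's remark that its estimate is conservative concerns the simplified risk classes, not the choice of cohort.

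**Stronger readings that the documents do not support.**
- A reader might infer that no analysis by disease group is planned. The SAP's definition of preexisting respiratory disease says that patients will be split into low, medium and high risk for analysis. What is missing is a defined pre/post contrast, and power, for those groups.
- A reader might take 27% as the power for hypothesis 2. That hypothesis is about the incidence of complications, and PACU time is not one. The figure bears on the primary endpoint in a subgroup. It also depends on an SD of 1,321.46 in 439 high-risk patients, and the plan allows a log-linear model.
- A reader might conclude that the deep-blockade cases should be removed. Section 26.0 is provisional there, and some of those cases could already meet two section 12.1 criteria. The passages need reconciling; whom the pathway should treat is not a statistical question.

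**Conclusion.** The concern holds in this form: the 90% power is correct for the whole one-year cohort and does not carry over to the prospective pathway comparison. Power for the printed differences at alpha 0.025 is about 59% (PACU time) and 63% (SpO2<90%) with 6,500 per period. In OSA/respiratory patients alone it is about 25% to 46% for SpO2<90%.

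These figures assume the plan's SD and effects, two-sided tests, and equal periods except where step 3 sets the full baseline year against 6,500. The 6,500-patient figures also assume the overall event rate. The disease-only figures rest on back-calculated denominators, and a larger true effect in that group would raise them. The different alpha in the SAP does not change the conclusion. Hypothesis 1, on the introduction of sugammadex in the whole population, is not affected.

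**What to change.** 1. Reconcile the population in hypothesis 2, sections 6.0 and 12.1, and section 26.0, including the deep-blockade cases. Section 12.1 lists surgery at a study site among its one-or-more criteria, which read literally would admit nearly everyone; the synopsis instead makes surgery elsewhere an exclusion. Settle this before any count is run.
2. Apply the reconciled criteria to the baseline year in the data warehouse. Recompute the number of patients, SD, event rate and power or detectable difference, and print these for the prospective part in place of the whole-cohort figures.
3. Pre-specify one pre/post estimate with a confidence interval in medium + high (OSA or respiratory disease) patients, and state its own detectable effect.

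The cost is wording, one query and one extra estimate; OSA and lung disease are already collected under section 17.0. The drawback is that the stated power will look less favourable.

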10.0 STUDY ENDPOINTSVariables/Time Points of Interest

- 1) **PACU Discharge Time (primary endpoint):** The duration in minutes from patient arrival in PACU until the ready for discharge order is placed by the anesthesiologist. This captures the time until they are clinically ready for discharge and eliminates noise such as the availability of beds that might effect actual discharge time
- 2) **Incidence of oxygen saturation <90%:** A binary variable indicating if the patient had any oxygen saturations below 90% from arrival in PACU until being marked for discharge
- 3) **Incidence of oxygen saturation <95%:** A binary variable indicating if the patient had any oxygen saturations below 95% from arrival in PACU until being marked for discharge
- 4) **Duration of supplemental oxygen use in PACU:** The total time in minutes that a patient received supplemental oxygen from arrival in PACU until being marked for discharge
- 5) **Reintubation rate:** The incidence of patients who required reinsertion of an endotracheal tube after the patient was extubated in the OR. This includes patients who were reintubated in the PACU or subsequently after PACU discharge.
- 6) **Unplanned Upgrade of Care:** The incidence, defined as a binary variable, of patients who were transferred to an ICU after being admitted to a non-ICU setting.
- 7) **Obstructive Sleep Apnea (OSA):** The presence of obstructive sleep apnea based upon previous structured data in the electronic medical record (EMR) such as prescriptions for CPAP, medical history and the anesthesiologist's preoperative note.

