3.0 PROTOCOL SUMMARY

Sponsor	Merck & Co., Inc.
Protocol Title	A prospective digital quality improvement project to apply best clinical practices to patients at high risk of respiratory complications
Drugs	The following FDA cleared drugs will be used in this study: 
 • Sugammadex
Study Objectives	Primary Objective 
 1) Time to “fitness for discharge” from the recovery room, as noted by the time the anesthesiologist places the discharge order, before and after intervention.

	
2) Incidence of hypoxemia in the PACU before and after intervention as defined by documentation oxygen saturation below 90%
 
Secondary Objectives
 
 1) Performance of identified best practices before and after intervention. 2) Incidence of hypoxemia in the PACU before and after intervention as defined by documentation of oxygen saturation below 95% 3) The duration of supplemental oxygen needed by high risk patients before and after intervention 4) Postoperative reintubation rate 5) Unplanned upgrade of care (defined as patients who are sent to the ICU after being admitted to a regular ward)
Study Design	Historical prospective comparative effectiveness trial
Study Phases	
Retrospective Data Analysis
 
Perform a retrospective analysis on data contained in our data warehouse on the incidence of respiratory dysfunction in the post-operative care unit (PACU) before and after the introduction of sugammadex into clinical practice.
 
Respiratory depression pathway implementation
 
Develop and implement a clinical best practice pathway designed to prevent postoperative respiratory complications in higher risk patients (such as those with OSA or preexisting respiratory disease) using education and clinical decision support in patients.

Sample Size	~13,000 retrospective and ~6,500 prospective
Clinical Sites	Ronald Reagan UCLA Medical Center, UCLA Santa Monica Hospital
Study Population	RRUMC or UCLA Santa Monica patients aged 18 and older who had a general anesthetic with either rocuronium or vecuronium.
Inclusion Criteria	
One or more:
 
 • Obstructive or restrictive lung disease in EMR • OSA • Preoperative O2 sat <95% (avg/median of 12 hours before surgery) • BMI > 40 • Acute respiratory infection within 1 month prior to surgery

[figure not shown]

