36.0 APPENDIX A - LIST OF STUDY INVESTIGATORS

Sites and investigators subject to IRB approval and subject to change without requiring protocol amendment.

Principal Investigator	[name] Dept. of Anesthesiology and Perioperative Medicine Ronald Reagan Hospital, University of California Los Angeles Email: [contact]
Other Site Investigators	[name]
	[name]
	[name] PhD
	[name]
Study Coordinators	[name]
	[name]

Statistical Analysis Plan

Variables/Time Points of Interest

Overall a variety of variables may be used for patient risk stratification, or creation of the propensity score. The majority of these have standard definitions and are listed above. The list below includes key variables used as inclusion criteria and or outcomes.

- PACU Discharge Time (primary endpoint): The duration in minutes from patient arrival in PACU until the ready for discharge order is placed by the anesthesiologist. This captures the time until they are clinically ready for discharge and eliminates noise such as the availability of beds that might effect actual discharge time
- Incidence of oxygen saturation <90%: A binary variable indicating if the patient had any oxygen saturations below 90% from arrival in PACU until being marked for discharge
- Incidence of oxygen saturation <95%: A binary variable indicating if the patient had any oxygen saturations below 95% from arrival in PACU until being marked for discharge
- Duration of supplemental oxygen use in PACU: The total time in minutes that a patient received supplemental oxygen from arrival in PACU until being marked for discharge
- Reintubation rate: The incidence of patients who required reinsertion of an endotracheal tube after the patient was extubated in the OR. This includes patients who were reintubated in the PACU or subsequently after PACU discharge
- Unplanned Upgrade of Care: The incidence, defined as a binary variable, of patients who were transferred to an ICU after being admitted to a non-ICU setting.
- Obstructive Sleep Apnea (OSA): The presence of obstructive sleep apnea based upon previous structured data in the electronic medical record (EMR) such as prescriptions for CPAP, medical history and the anesthesiologist's preoperative note.

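### The SpO2 <90% co-primary is counted only until the discharge order, so a shorter time to that order (the other primary endpoint) can lower recorded hypoxemia with no change in risk

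*Combined protocol and SAP*

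**What the plan says.** Protocol Section 10.0 defines PACU discharge time, labelled the primary endpoint, as "The duration in minutes from patient arrival in PACU until the ready for discharge order is placed by the anesthesiologist". Section 3.0 lists hypoxemia below 90% as a second primary objective, and Section 25.1 splits alpha across two primary outcomes. Section 10.0 counts that hypoxemia as "any oxygen saturations below 90% from arrival in PACU until being marked for discharge", and the SAP list of variables repeats it: "A binary variable indicating if the patient had any oxygen saturations below 90% from arrival in PACU until being marked for discharge". SpO2 <95% ends at the same point. So does supplemental oxygen: "The total time in minutes that a patient received supplemental oxygen from arrival in PACU until being marked for discharge". Section 3.0 gives no end to the window, only "Incidence of hypoxemia in the PACU before and after intervention as defined by documentation oxygen saturation below 90".

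Section 10.0 prefers the order to actual departure because it "eliminates noise such as the availability of beds that might effect actual discharge time". Patients can therefore still be in the PACU after the order, and their readings from then on are not counted.

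The analysis (Section 25.1 and SAP Statistical Methods, carried into the prospective part by Section 25.2) is a logistic regression on propensity-matched data plus a segmented regression. Neither document plans a fixed window, a person-time or time-to-first-event analysis, or a sensitivity analysis for length of observation.

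**The concern.** An indicator of at least one low reading depends on how long the patient is watched. Here the length of watching is an outcome that the study hopes to shorten. Matching balances characteristics of the patients; it cannot equalise an observation time that is set after surgery by a clinician's order.

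The design leaves room for this to happen. It is an unblinded comparison with a one-year historical baseline, and clinicians are trained on the pathway before go-live (Section 8.0). A drift in when the order is placed would change the window even if nothing changed in the patients. A favourable hypoxemia result could then be a real reduction, a shorter window or a mixture, and the planned analyses could not tell these apart.

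**Working it through.** **Inputs.** From Section 26.0: mean PACU discharge time T = 152.54 min (SD 623.86); SpO2 <90% in 574/12,467 = 4.6%; detectable reduction in discharge time 27.04 min; detectable hypoxemia rate "if it decreases to around 3.7% in the post", both at 90% power and alpha 0.025. Table 2 in that section gives n = 13,277 overall. Assumed, because the documents do not say: two-sided tests, two periods of equal size, the timing of first desaturations within the stay, and an equal cut to every stay.

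**Step 1: the plan's own figures.**
- Discharge time: (z0.9875 + z0.90) × SD × √(2/n) = 3.523 × 623.86 × √(2/13,277) = 26.97 min, against 27.04 stated.
- SpO2 <90%: 4.6% versus 3.7% with 12,467 per period gives 90.7% power by the chi-square approximation.

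Both reproduce. The benchmark is 4.6% − 3.7% = 0.9 points.

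**Step 2: constant hazard, risk unchanged, every stay 27.04 min shorter.**
- New window: 152.54 − 27.04 = 125.50 min.
- Rate: 1 − (1 − 0.046)^(125.50/152.54) = 3.80%.
- Artefact: 0.80 points, and 0.80/0.9 = 89% of the detectable drop.
- Chance of p < 0.025 from this alone: about 82% with 12,467 per period, or about 63% with 6,500 in the later period.

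**Step 3: front-loaded hazard.** Let the hazard decay exponentially with half-life h, k = ln2/h, scaled to give 4.6% at 152.54 min. The share of cumulative hazard left after the cut is f = (1 − e^(−125.50k))/(1 − e^(−152.54k)), and the rate is 1 − (1 − 0.046)^f.

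| Half-life (min) | f | Rate | Drop (points) | Share of 0.9 | Chance of p < 0.025 (12,467 per period) |
|---|---|---|---|---|---|
| constant | 0.823 | 3.80% | 0.80 | 89% | 82% |
| 120 | 0.880 | 4.06% | 0.54 | 60% | 44% |
| 60 | 0.924 | 4.26% | 0.34 | 38% | 18% |
| 30 | 0.974 | 4.48% | 0.12 | 13% | 4% |
| 10 | 1.000 | 4.60% | 0.00 | 0% | 1.3% |

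The last 1.3% is the nominal one-tail level, so there is no excess.

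**Step 4: unequal shortening.** The SD is about four times the mean (623.86/152.54 = 4.1), so a few very long stays may drive the mean. As an illustration only, take a lognormal stay with the stated mean and SD, a constant hazard, and the same fall in the mean produced by capping the longest 1.5% of stays. The rate falls only to 4.30%, with about a 14% chance of significance.

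**The case against.** The strongest reply is that a shorter window lowers an any-event indicator only for patients whose first low reading would have fallen in the removed minutes. Those minutes are the last before a clinician judges the patient ready to leave, so constant hazard is the least plausible case. This stands, and it is why the range reaches down to zero. The skew in length of stay (step 4) points the same way.

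A reader might infer that any shortening of the stay must lower the hypoxemia rate. The documents do not support that. A shorter window cannot raise the recorded rate, but whether it lowers it depends on event times that are not given. The same caution applies to oxygen duration: mean use is 74.81 min against a mean stay of 152.54 min (Table 2), and an earlier order cuts oxygen minutes only for patients still on oxygen when it is placed. No size was worked out for that endpoint or for SpO2 <95%.

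A reader might also infer that a joint fall in both primaries would expose an artefact. It would not. Hypoxemia can itself delay the order, so a real benefit would also move both.

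Finally, the Bonferroni split in Section 25.1 is valid however the two endpoints are related, and reintubation is expressly followed past PACU discharge. Both points are correct, but neither corrects the observation time of the SpO2 endpoint.

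**Conclusion.** The point holds as a possible bias of unknown size in one of the two primary endpoints. Both documents end the SpO2 <90% window at the event that defines the other primary, and nothing planned adjusts for it. At the study's own detectable shortening, with no change in risk, the artefact runs from nothing to about 90% of the detectable hypoxemia effect. That range rests on the assumed hazard shapes and on every stay shortening equally; it is smaller if the mean falls through a few extreme stays. The documents support saying that a shorter time to order can lower recorded hypoxemia, not that it must. This should be dealt with, because the upper end is close to the design effect and the plan offers no way to find out where in the range the study lies.

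**What to change.** Keep the arrival-to-order endpoint. Beside it, pre-specify in the SAP a sensitivity analysis of SpO2 <90%, SpO2 <95% and oxygen duration over a fixed window from PACU arrival, identical in both periods and counted whether or not the order has been placed.

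- **Window length.** Choose it from baseline-year stay data, before prospective outcomes are seen, so that nearly all patients are still observed in the PACU at its end. The documents give no median or quantiles of stay, so no length can be recommended from them. The lognormal illustration in step 4 has a median near 36 min and about 62% of orders placed before 60 min, which shows why a round figure should not be assumed.
- **Early leavers.** Censor at actual PACU departure, with time to first event for the two binary outcomes, and report how many are censored in each period.
- **Reporting.** If the two versions disagree, do not report the arrival-to-order result as a reduction in hypoxemia risk without that qualification.
- **Wording.** Align Section 3.0 (no end of window) and Section 25.1 with its SAP counterpart (which call the outcome a duration below 90% but analyse it as binary) with Section 10.0.

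The cost is SAP text and one extra warehouse query. Section 17.0 collects durations below each threshold and Section 29.2.1 builds each element from raw clinical data, so timed readings are probably available, but this should be confirmed for the minutes after the order. The downside is that events after the window are not counted in that version and some patients are censored.
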